In Vivo Pulse Oximeter Validation Study

Test Protocol

NCT05873335

February 2, 2023

Hypoxia Lab

Principal Investigators:

- [name] MD. PhD
- [name]

The Hypoxia Research Laboratory at UCSF laboratory has developed methods that permit the performance testing of pulse oximeters, enabling collection of data for submission to the FDA for device clearance or for engineering development of the devices. The basics of the protocol involve brief stable arterial oxygen desaturation in healthy volunteers and sampling arterial blood when a stable level of hypoxia has been attained. The blood sample is analyzed for oxygen saturation with a gold standard bench CO-oximeter, currently a Radiometer ABL-90. This document describes the program and arrangements. 6 to 8 subjects can be studied in a single day, with 20-25 arterial blood samples from each subject.

Subjects

Ten to 12 subjects can be studied over two days, also with 20-25 arterial blood samples each. This protocol is aligned with the latest ISO and FDA guidance documents for pulse oximeter testing. 10 subjects can be studied in one day if no blood draws are planned.

Methods

The key to obtaining stable, safe and controlled hypoxia is breath-by breath by breath respiratory gas analysis and a computer program that permits the inspired gas mixture to be adjusted to achieve a level of lung alveolar gas that will achieve the desired degree of hypoxia. Typically, saturation is determined once with air breathing and then at one of 6 levels, e.g. 94%, 90%, 85%, 80%, 75% and 70% saturation for about 30-60 seconds at each level. During Aim 1 and aim 2, an arterial blood sample is obtained from an indwelling catheter at the end of each hypoxic plateau. The operator changes the inspired oxygen concentration at the end of each blood sampling to attain the next desired stead-state conditions hypoxia. A "run" takes 10-15 minutes, and each run is terminated by a breath of 100% O2 followed by room air. Two runs together enable obtaining a total of 20-25 blood samples, 2 samples at each different plateau. Saturation of each arterial blood sample is determined by direct oximetry in a Radiometer ABL-90 multi-wavelength oximeter. The precise target levels of saturation can be adjusted to suit the sponsor, but typical testing is done to satisfy ISO and FDA standards for testing, which is 70% to 100%.

Data from test pulse oximeters for comparison to blood values can be obtained in several ways. In every case, the goal is to obtain a reading from the oximeter that corresponds to the associated blood sample or a reference oximeter. Because of circulation delays and instrument averaging time, we attempt to create steady state conditions at each level of oxygenation. Therefore, a means should be provided to record the instrument reading at each blood sample. This instrument reading may be obtained with several different approaches. Some instruments have no digital or analog output and the instrument reading may be recorded manually or recorded by a video of the instrument display. Other instruments may have an analog output. The laboratory can record analog data by use of LabView. Digital recording of output can also be obtained via LabView but his requires information from the sponsor concerning the structure of the digital signal. Consultation with us is recommended.

If a manufacturer prefers to collect and analyze the data, the continuous digital signal of each oximeter should be read, for comparison with the blood sample, 9 seconds before the record shows a sudden fall or rise in oxygen saturation, not at the time of blood sampling. This procedure accounts for the delays of finger circulation and uses the estimated delay from the lung to the sample site. There is no useful correlation between the actual time of blood sampling and the oximeter recording because of the variability of tissue blood flow lag. As mentioned, steady-state hypoxia avoids the concern that oximeter reading is not aligned with a blood sample reading.

We enroll only healthy subjects between the ages of 18 and 55 in the studies. The study takes about 1 hour of each subject's time. Analysis of the data requires several days. We encourage manufacturer's

representatives to be present for these tests, and to mount the probes. An extra charge is made if no representative is present, requiring us to mount the probes and record data.

Sites for affixing pulse oximeter probes may include the fingers, wrist, ears, forehead or other flat body surfaces and the nose. Special testing, with various conditions or with special subject populations can also be arranged, at extra charge.

We also offer testing for performance during controlled subject hand motion. Three types of motion are typically used: tapping, rubbing and random motion. Tapping and random motion are done with a computer-controlled motion machine.

Testing during low perfusion conditions is also available at an extra charge. In all cases, the blood analysis data are provided, including the SaO2, MetHb, COHb and Hgb concentration.

Data Analysis:

The data analysis report will consist of the following:

- A Table of the oximeter readings versus corresponding blood SaO2 values.
- Graphic plots of the bias between the oximeter reading and the SaO2 measured by the hemoximeter (on the blood sample, i.e Modified Bland -Altman plots for each instrument or instrument probe combination.
- Regression equations for the bias of each instrument.
- Tables of the mean error or bias, its standard deviation, standard error, 95% confidence interval, maximum and minimum and root mean square error, all computed both overall and by several sub-ranges of desaturation.
- A table of the demographics of the subject population is provided.

These studies are done with approval of the UCSF Committee on Human Research. Informed consent is obtained from each subject. The UCSF Hypoxia Laboratory conforms to Good Clinical Practice Standards for the involvement of human subjects and handling of test data.

Manufacturers must provide their own pulse oximeters and probes. Each individual manufacturer is charged an amount determined by the number of subjects, the number of samples per subject, and the number of oximeters plus the departmental and UCSF overhead charges.

Statistics

The number of subjects and the number of comparisons (paired pulse oximeter readings and arterial saturation values) is determined by current FDA guidance requirements (*Pulse Oximeters - Premarket Notification, 2013*). This is a minimum of 200 data points and 10 subjects. During this type of study, some subjects may drop out, some readings can be lost due to motion or other interference and occasionally some do not consent.

The following demographic data will be collected on the subjects:

- gender
- age
- skin tone (dark/medium/light and Fitzpatrick scale)
- height (cm)
- weight (kg)

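### For instruments without an output, hand-recorded readings are accepted on equal terms with video and no verifiable record is required, so selective reading toward the plateau target could not be checked

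*Combined protocol and SAP*

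**What the plan says.** The Methods section asks that "a means should be provided to record the instrument reading at each blood sample". For devices with an analog or digital output it describes capture through LabView. For the rest, it says that "the instrument reading may be recorded manually or recorded by a video of the instrument display". It states no preference between the two, and specifies no second reader, masking of the recorder or retained image of the display.

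On who records, the plan is indirect. It encourages manufacturer's "representatives to be present for these tests, and to mount the probes", which does not mention recording. It then adds: "An extra charge is made if no representative is present, requiring us to mount the probes and record data".

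Plateau levels are set beforehand, for example "94%, 90%, 85%, 80%, 75% and 70% saturation for about 30-60 seconds at each level", and "The precise target levels of saturation can be adjusted to suit the sponsor". The reference is measured, not nominal: "Saturation of each arterial blood sample is determined by direct oximetry in a Radiometer ABL-90 multi-wavelength oximeter". The Data Analysis section reports bias, its SD, extremes and RMSE, overall and by saturation sub-range. Its only statement on data integrity is general conformity with Good Clinical Practice, including the handling of test data.

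**The concern.** A display can move during a plateau of 30 to 60 seconds, and a live reader has to settle on one number. That reader is not masked and probably knows the target, since targets are preset and the sponsor may have had them adjusted. Gas mixtures are steered to bring SaO2 to the target, so drift of the written value toward the target is mostly drift toward the reference. Unconscious preference for the closer value would then shrink the apparent error.

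The data may support a device clearance submission, and every accuracy statistic in the report depends on the written number. Hand-read devices would also not be comparable with digitally captured ones. If only a handwritten number exists, the display values that were passed over cannot be recovered afterwards.

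**Working it through.** **The plan's own figure.** The concern disputes no number in the plan. The Statistics minimum of 200 pairs from 10 subjects follows from the 20 to 25 samples per subject: 10 × 20 = 200 and 10 × 25 = 250. For an instrument without output, nothing prevents all of these pairs from being handwritten.

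**How each route fixes the reading.**
- Continuous digital signal analysed by the manufacturer: a stated point, 9 seconds before the abrupt change in saturation.
- Instrument without output, by hand or video: only that a reading be captured at each blood sample. The 9-second rule is not extended to these devices. The paragraph that gives it also says that the time of blood sampling does not usefully track the oximeter recording.
- Re-reading: possible from video, not from a handwritten value alone.

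**Size, by simulation.** All inputs are assumptions; the documents give none.
- SaO2 = target + scatter (SD 1 to 3).
- Displayed value = SaO2 + device error (SD 1.8) + jitter (SD 0.3 to 1.0), rounded to a whole number.
- Without selection, one displayed value is written. With selection, the one nearest the target among two or three is written.
- Error is always taken against SaO2, not the target. There were 400,000 plateaus per setting.

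Check on the unselected value: RMSE = √(device² + jitter² + 1/12), where 1/12 is the rounding variance. With jitter 1.0 this is √(3.24 + 1.00 + 0.083) = 2.08, as simulated.

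| Jitter SD | SaO2 scatter SD | Plateaus with selection | No selection | Nearer of 2 | Nearest of 3 | Reduction |
|---|---|---|---|---|---|---|
| 1.0 | 1 | 100% | 2.08 | 1.66 | 1.49 | 20–28% |
| 0.7 | 1 | 100% | 1.95 | 1.67 | 1.54 | about 15–21% |
| 1.0 | 3 | 100% | 2.08 | 1.84 | 1.77 | about 12–15% |
| 0.3 | 1 | 100% | 1.85 | 1.73 | 1.67 | about 7–10% |
| 0.3 | 3 | 100% | 1.85 | 1.78 | 1.75 | about 4–5% |
| 1.0 | 1 | 25% | 2.08 | 1.98 | 1.95 | about 5–6% |
| 0.5 | 2 | 25% | 1.89 | 1.85 | 1.84 | about 2–3% |

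If successive displayed values are correlated at 0.8 (jitter 1.0, scatter 1, selection everywhere), the reduction is 9–13%.

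Partial selection mixes mean squares. With jitter 1.0 and scatter 1, 25% selection between two values gives √(0.75 × 2.08² + 0.25 × 1.66²) = √3.93 = 1.98. The mildest corner (jitter 0.3, scatter 3, 25%) gives √(0.75 × 1.85² + 0.25 × 1.78²) = 1.83, about 1% below 1.85.

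**A second model.** Suppose the written value is (1 − w) × reading + w × target, with the target unbiased for SaO2. Reported RMSE is then √((1 − w)²A² + w²s²), where A is the true RMSE and s the SaO2 scatter. For A = 3.0 and w = 0.10, s = 1 gives √(7.29 + 0.01) = 2.70 and s = 3 gives √(7.29 + 0.09) = 2.72. The benefit to the device is limited by the scatter: with A = 2.0 and s = 3, w = 0.25 gives 1.68, but w = 0.50 gives 1.80.

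**The case against.** The strongest reply is that the design already limits the mechanism. Error is taken against bench SaO2 on the blood sample, so moving toward the target helps only as far as SaO2 lies near it. The plan aims for steady state and mentions instrument averaging, so a display on a good plateau should change little. Both points stand, and they are why the reduction falls to a few percent with small jitter or wide scatter. The 20–28% case needs selection at every plateau, independent displayed values, jitter SD 1.0 and tight SaO2 control, so it lies near the worst case.

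A reader might also infer more than the text supports:
- That no source record exists. A manual entry is a record, although it cannot be verified independently, and video is offered and can be re-read.
- That the representative records by default. No sentence assigns manual reading to that person. The extra-charge sentence implies only that an attending representative may record, and it covers every kind of data capture.
- That the recorder knows the target at each reading. This is likely but not stated; the listed levels are examples, and it is the operator who changes the inspired oxygen.

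The Good Clinical Practice statement is a fair point for the plan, but it names no control over this step.

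Finally, requiring video does not by itself remove discretion. Without a defined reading time a video reader must also choose a value, and masking to SaO2 does not mask the target. This objection stands and shapes the fix.

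**Conclusion.** The concern holds in a limited form. For instruments without output, the plan accepts unverified manual readings on the same footing as video, and a manufacturer's representative who is present apparently may take them. For a manual-only data set it provides no means to detect or exclude reading toward the target.

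If such selection happened, reported RMSE would be lowered in every simulated setting, by about 2–28% across most of the assumed range and about 1% at its mildest corner. That range rests wholly on assumed device error, jitter, scatter and frequency of selection. It does not show that any result is biased, and the documents do not support the stronger inference that RMSE for hand-read devices is in fact optimistic. Data sets captured on video can be re-read and do not have this verification gap, though their reading time is equally undefined. The change is still worth making before data collection, because the plan already lists the remedy and lost display values cannot be rebuilt.

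**What to change.** In Methods, for instruments without analog or digital output:

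- Require video of the display as the source for accuracy pairs, kept by the laboratory and carrying the session clock. A manual note may serve as backup.
- Fix in advance one reading time for these instruments, relative to each blood draw or plateau end. The current text gives none.
- Have existing laboratory staff transcribe the value shown at that time, before SaO2 values are merged.
- Leave representatives free to mount probes and take notes; they need not be barred from either.

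The cost is a short addition to Methods, one camera per display and some transcription time. No additional reader is needed, and the number of subjects and samples does not change.

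### The standard error and 95% CI for mean bias come from 20-25 repeated pairs in each of 10-12 subjects, and the plan makes no allowance for dependence within subject

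*Combined protocol and SAP*

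**What the plan says.** **Number of pairs.** The Statistics section counts comparisons, each being an oximeter reading paired with an arterial saturation, and sets a floor of 200 from at least 10 subjects. The Subjects section foresees 10 to 12 subjects over two days. Methods gives the yield per subject: "Two runs together enable obtaining a total of 20-25 blood samples, 2 samples at each different plateau".

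**Summary statistics.** The Data Analysis section lists, for mean bias, an SD, standard error, 95% confidence interval, range and root mean square error, both overall and by sub-range of desaturation. It gives no formula for the standard error or interval, and does not mention subject, run or plateau as a source of variation.

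**Sampling and pairing.** Methods also says that "an arterial blood sample is obtained from an indwelling catheter at the end of each hypoxic plateau", and that "The operator changes the inspired oxygen concentration at the end of each blood sampling". In general a reading is to be recorded at each blood sample. If the manufacturer collects and analyses the data, the signal is instead to be read "9 seconds before the record shows a sudden fall or rise in oxygen saturation, not at the time of blood sampling".

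**The concern.** At least 200 pairs from about 10 people are not 200 independent observations. A subject whose finger, skin or probe fit makes the device read high will tend to give high readings at many of the 20-25 samples. Pairs from one plateau would be closer still, and if they share one oximeter reading they also share its error.

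A standard error computed as if all pairs were independent ignores this and would generally be too small, with the 95% interval too narrow. Methods says that the laboratory's data may support a device submission or engineering work, so a reader of the report could take mean bias to be known more precisely than it is. The issue arises whoever records the readings. The point estimate of bias is not the problem: with similar numbers of pairs per subject, the plain mean is close to the mean of the subject means.

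**Working it through.** **1. The plan's own count.** Pairs = subjects x samples per subject.
- 10 subjects: 10 x 20 = 200 to 10 x 25 = 250
- 12 subjects: 12 x 20 = 240 to 12 x 25 = 300

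The stated minimum of 200 is reproduced when each blood sample gives one pair, with no reserve at 10 subjects and 20 samples.

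**2. Effect of clustering on the standard error.** With m pairs per subject and a common correlation r between errors in the same subject, the variance of the mean is inflated by 1 + (m - 1) x r. The standard error is understated by the square root of that. Here m = 20 or 25 comes from the Methods section. The documents give no r, so r = 0.05 to 0.5 is an assumption.

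| m | r | 1 + (m - 1) x r | SE understated by |
|---|---|---|---|
| 20 | 0.05 | 1 + 19 x 0.05 = 1.95 | 1.40 |
| 25 | 0.05 | 1 + 24 x 0.05 = 2.20 | 1.48 |
| 20 | 0.5 | 1 + 19 x 0.5 = 10.5 | 3.24 |
| 25 | 0.5 | 1 + 24 x 0.5 = 13.0 | 3.61 |

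For 10 subjects, 200 pairs at r = 0.05 carry the information of 200/1.95, or about 103 independent pairs. At r = 0.5, 250 pairs carry that of 250/13, or about 19. The factor depends on m and r, not on the number of subjects, so 12 subjects do not remove it.

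**3. Sub-ranges.** Each subject has fewer pairs in a sub-range, so m is smaller and the factor falls for the same r. The correlation may differ within a narrow range. The documents give neither figure, so this is not quantified.

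**4. Samples per plateau (minor clarification).** Methods describes the levels thus: "Typically, saturation is determined once with air breathing and then at one of 6 levels". Samples per subject = 2 runs x plateaus per run x samples per plateau + air samples.
- Six plateaus, one sample each: 2 x 6 x 1 = 12, plus 1 or 2 air samples = 13-14, short of 20-25.
- Six plateaus, two samples each: 2 x 6 x 2 = 24, plus 1 air sample = 25, which fits. With 2 air samples it is 26, just outside.
- Single-sample plateaus: 2 x 9 + 2 = 20 to 2 x 12 + 1 = 25, so 9-12 per run reach 20-25. The plan gives "saturation for about 30-60 seconds at each level", so these take 9 x 0.5 = 4.5 to 12 x 1 = 12 minutes of plateau time. That can fit a run of 10-15 minutes. Visiting each of six levels twice per run, with one sample per visit, is one such layout.

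**5. Readings on the manufacturer route.** Each plateau ends in one step in saturation; for the last, "each run is terminated by a breath of 100% O2 followed by room air". The 9-second rule therefore gives one reading per plateau. With single-sample plateaus every sample has its own reading. With two samples on an uninterrupted plateau, both would have to use that reading or some other rule, and none is stated.

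**The case against.** **The plan does not say that pairs are treated as independent.** This is true. It gives no formula, so a clustered calculation is not excluded. But nothing in the text asks for one, and a standard error listed beside an SD and a pair count would ordinarily be read as SD over root n. A reader might infer that the reported intervals are wrong; the documents show only that the method is left open. Nor do they say that the laboratory's report is produced when the manufacturer does the analysis.

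**The size is assumed.** This is also true. If within-subject correlation were close to zero, the understatement would be small. But at the lower end of the assumed range, with 20 pairs per subject, the factor is already 1.4.

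**The shared-plateau gap is narrow.** This stands. It needs the optional manufacturer route and two samples on one uninterrupted plateau. One sample per plateau with a gas change after each sampling is the more literal reading of Methods, and two samples per level could mean one from each run. Six levels are only typical: "The precise target levels of saturation can be adjusted to suit the sponsor". The steady-state argument in Methods also supports using the plateau reading for either sample.

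**A stronger reading is tempting.** A reader might infer that 10-12 subjects could miss 200 pairs on that route, because two runs of six plateaus plus one air reading give 13 distinct readings per subject: 130 for 10 subjects and 156 for 12. This needs a rule that each reading counts only once, and no such rule appears in the documents. The Statistics section counts readings paired with arterial values. On that wording two arterial values, each compared with a reading, are two comparisons, so 25 samples per subject give 250-300.

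**Conclusion.** The point holds as a gap in the precision statement. The plan promises a standard error and 95% interval for mean bias from 20-25 pairs in each of 10-12 subjects, and provides no allowance for dependence within subject, or within plateau where samples share one. If pairs are treated as independent, the standard error is understated by a factor of about 1.4 to 3.6. This rests on an assumed common within-subject correlation of 0.05-0.5 and on similar numbers of pairs per subject. Mean bias should change little.

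The samples-per-plateau wording and the pairing rule on the manufacturer route need clarifying, but that is minor. The documents do not support the inference that the 200-pair minimum is at risk from reading reuse, or that more subjects are needed for that reason.

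**What to change.** **Main change, in the Data Analysis section.**
- Label each row of the readings table with subject, run and plateau.
- Compute the standard error and 95% interval for mean bias, overall and by sub-range, with a random effect for subject (and for plateau within subject where samples share one), or with a bootstrap that resamples whole subjects.
- State which method is used. With about 10 subjects either is approximate, so the number of subjects should be shown beside the number of pairs.

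**Minor clarification, in the Methods section.**
- State plateaus per run, samples per plateau and air samples so that they add up to 20-25.
- State which reading goes with each sample on the manufacturer route if two samples share a plateau.

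**Cost.** Wording, row labels and a standard clustered analysis of data already being collected. No extra blood samples or subjects are needed. The downside is that the interval will probably be wider.

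### Does allowing sessions without blood draws leave the sample-size basis and the accuracy report without a usable definition?

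*Combined protocol and SAP*

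**What the plan says.** The Subjects section lists how many people the laboratory can handle. Ten to 12 can be studied over two days with 20 to 25 arterial samples each, and "10 subjects can be studied in one day if no blood draws are planned". Methods then says: "During Aim 1 and aim 2, an arterial blood sample is obtained from an indwelling catheter at the end of each hypoxic plateau". The aims are not defined anywhere.

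The part of Methods on data from test oximeters states that in every case "the goal is to obtain a reading from the oximeter that corresponds to the associated blood sample or a reference oximeter". It continues: "Therefore, a means should be provided to record the instrument reading at each blood sample". For manufacturers who collect their own data, it gives a separate rule: read the continuous signal 9 seconds before the trace shows an abrupt change in saturation, and not when blood is drawn.

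In Data Analysis, "The data analysis report will consist of the following" introduces five items. The first is "A Table of the oximeter readings versus corresponding blood SaO2 values". The second is "Graphic plots of the bias between the oximeter reading and the SaO2 measured by the hemoximeter". The third is regression equations for bias. The fourth is tables of mean error or bias with its spread, confidence interval and root mean square error. The fifth is demographics.

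Statistics sets the size: "the number of comparisons (paired pulse oximeter readings and arterial saturation values) is determined by current FDA guidance requirements". The stated minimum is 200 data points and 10 subjects.

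**The concern.** The protocol appears to open a route that its analysis does not follow through. Methods admits a comparator other than blood, and Subjects admits a day without draws. Neither Data Analysis nor Statistics mentions a reference oximeter, and neither says that it covers only sessions with arterial sampling. Limiting sampling to two aims suggests that work outside those aims exists.

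If such a session were run under this plan, its subjects would be desaturated without a stated size basis. The model of the reference oximeter and, for data recorded by the laboratory, the moment of reading would be settled later, perhaps once data were visible. The results might also appear under the same bias and root mean square error headings as the arterial results, although they measure a different quantity. In a document meant to support regulatory submissions, that would be a labelling error of some consequence.

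**Working it through.** **Inputs.** From Subjects: 10 to 12 subjects over two days, 20 to 25 arterial samples each; or 10 subjects in one day with none. From Statistics: at least 200 pairs and 10 subjects, a pair being an oximeter reading with an arterial saturation. From Data Analysis: the five report items.

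**1. The plan's own figure.** Pairs = subjects × arterial samples per subject.

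| Subjects | Samples each | Arterial pairs |
|---|---|---|
| 10 | 20 | 200 |
| 10 | 25 | 250 |
| 12 | 20 | 240 |
| 12 | 25 | 300 |

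The smallest combination reproduces the stated minimum of 200. The minimum comes from guidance. No alpha, power, standard deviation or margin is given, so there is no power calculation to check.

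**2. The no-draw day.** 10 × 0 = 0 arterial pairs. This only restates that no blood was taken. The 10-subject part of the minimum could still be met.

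**3. Could a no-draw subject be counted by mistake?** Suppose *k* of 10 subjects had no draws. The count is (10 − *k*) × 20 to (10 − *k*) × 25:

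- *k* = 1 gives 9 × 20 = 180 to 9 × 25 = 225.
- *k* = 2 gives 8 × 20 = 160 to 8 × 25 = 200.

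These subjects add nothing, because a pair must contain an arterial value. Any shortfall would show in the count, so the definition of a pair already limits the scope of the rule.

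**4. The report items.**

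| Item | Comparator named? | Without blood |
|---|---|---|
| Table of readings | Yes, blood SaO2 | Not possible |
| Bias plots | Yes, hemoximeter SaO2 | Not possible |
| Regression of bias | No | Possible against a reference oximeter, unless bias keeps the meaning given for the plots |
| Bias and root mean square error tables | No | Same |
| Demographics | None needed | Possible |

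The count that cannot be produced is 2 of 5 by explicit wording, and 4 of 5 if bias is read by its only definition.

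**5. Comparator and reading time.** Methods offers two comparators. Without blood, one remains, and only its model is unspecified. The 9-second rule is written for comparison with blood, but its time marker is the saturation trace, which exists with or without a draw. Methods also relies on steady plateaus to remove most of the alignment problem. What is missing is a reading rule written specifically for laboratory-recorded data without blood.

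**6. Is the quantity different?** Let *T* be the test reading, *R* the reference oximeter and *S* the arterial saturation. Then *T* − *R* = (*T* − *S*) − (*R* − *S*), the test device's error minus the reference's error. It needs its own label. It cannot contaminate the arterial estimates, because without *S* the difference *T* − *S* cannot be computed.

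**The case for a change.** The best case for a change is that the cost is a few words and the benefit is a clean boundary. Sampling is limited to two undefined aims, a second comparator is named, and the analysis text says nothing about either. Nothing written prevents a test-minus-reference difference from being tabulated under the same heading as error against SaO2. The introduction mentions engineering development as one use of the data but does not link it to the no-draw day, so a reader has to infer the link. The sentence saying that blood data are supplied in all cases states no exception for such sessions.

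Part of this stands. The aims are undefined, reference-oximeter results are not covered in Data Analysis or Statistics, and the two kinds of difference should not share a label.

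The rest is weaker. The no-draw sentence is one of several throughput figures in a document that describes a laboratory's program and arrangements. The statement about all cases directly follows the motion and low-perfusion options and may well refer only to them. A late choice of comparator is conjecture, since only one kind of comparator remains. The proposed clarification would also supply neither a reading time nor a size basis for no-draw sessions. It would only record scope and labels that a competent analyst would apply anyway.

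**Conclusion.** No change is needed. The plan leaves an optional session type undescribed, but no stated rule or number gives a wrong result. The 200-pair, 10-subject minimum reproduces as 10 × 20 and is sound for arterial sessions. The SaO2 bias and root mean square error tables are unaffected, because readings without an arterial value cannot enter them. The gap covers two report items explicitly, or four on the narrower reading of bias, and only for a session that the documents do not say will take place in this study.

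This rests on two assumptions. The first is that a no-draw day is a service the laboratory can arrange, not a counted part of this validation. The second is that anyone reporting such a day would describe it as agreement with a reference oximeter, as the definitions already imply. If no-draw data were presented as accuracy against SaO2, the fault would lie in that report, which would be departing from the plan's own definition of a comparison.

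### Does a report with no count of lost readings hide a device's failure to read under motion?

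*Combined protocol and SAP*

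**What the plan says.** The protocol's Statistics section takes its size from the cited guidance: at least 200 paired points and 10 subjects. It then mentions subject dropout and adds that "some readings can be lost due to motion or other interference and occasionally some do not consent". It gives no loss rate, no definition of a lost reading and no rule for rejecting a displayed value.

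The Data Analysis section opens with "The data analysis report will consist of the following" and lists five items: a table of readings against blood SaO2, modified Bland-Altman plots, regression equations for bias, tables of summary error statistics (including SD, SE and root mean square error, overall and by sub-range), and demographics.

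The end of the Methods section describes the optional work: "We also offer testing for performance during controlled subject hand motion", with three motion types, and "Testing during low perfusion conditions is also available at an extra charge". It then says: "In all cases, the blood analysis data are provided, including the SaO2, MetHb, COHb and Hgb concentration". Earlier, Methods asks that the device value be captured sample by sample: "Therefore, a means should be provided to record the instrument reading at each blood sample". The Subjects section notes that "10 subjects can be studied in one day if no blood draws are planned".

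**The concern.** Every listed accuracy output exists only where the device gave a reading. Under hand motion or low perfusion, a blank display is a failure of the device, yet the one sentence on lost readings sets them beside dropout and non-consent, as if they were only a drain on sample size. A device that always reads and one that blanks at one sample in five would have the same expected bias, SD and root mean square error if the blanks were unrelated to error. If difficult readings were preferentially lost or rejected, the accuracy figures would also look better than they should.

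The stakes are real, since the introduction describes the work as "enabling collection of data for submission to the FDA for device clearance". A narrower worry is that no validity criterion is written down, and nothing says that rejections, or later reading of traces or video, are made without sight of SaO2.

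**Working it through.** **1. The plan's own figure.** Subjects × samples per subject at the low end is 10 × 20 = 200, which reproduces the stated minimum. There is no power calculation to check.

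**2. Loss that would still meet 200 pairs.** Room for loss = planned pairs − 200.

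| Plan | Pairs | Room for loss |
|---|---|---|
| 10 × 20 | 200 | 0 |
| 12 × 20 | 240 | 40 (16.7%) |
| 10 × 25 | 250 | 50 (20%) |
| 12 × 25 | 300 | 100 (33.3%) |

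The minimum alone would therefore not expose a sizeable loss in the larger plans. No separate count is given for motion tests, so 250 is assumed below.

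**3. Loss unrelated to error.** Expected bias, SD and root mean square error do not move. Only the SE does, by √(250/pairs):
- 12 lost: √(250/238) = 1.025
- 25 lost: √(250/225) = 1.054
- 50 lost: √(250/200) = 1.118

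**4. Can a reader see the loss in the accuracy tables?** The report gives SD and SE together. If SE = SD/√pairs, then pairs = (SD/SE)². Chance variation in the SD cancels, because both figures come from the same data. With an assumed SD of 2.00 and the matching simulated mean SEs:

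| True pairs | SE | (2.00/SE)² |
|---|---|---|
| 250 | 0.126 | 252 |
| 238 | 0.129 | 240 |
| 225 | 0.133 | 226 |
| 200 | 0.141 | 201 |

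This route has two limits. An SE adjusted for repeated samples within subject would break the formula. Rounding also matters: an SE printed as 0.13 lies between 0.125 and 0.135, which allows (2.00/0.135)² = 219 to (2.00/0.125)² = 256 pairs. It is a useful check but not the main evidence.

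**5. Direct count.** The first report item tabulates readings against SaO2, and the blood results are supplied as well. Samples minus readings gives the total lost: 250 − 200 = 50, and 50/250 = 20% (exact 95% interval 15.2% to 25.5%, treating samples as independent, which 20 to 25 per subject are not). This needs no assumption about the SE. If the table keeps sub-range or test condition, the count can be split the same way.

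**6. Loss related to error.** Root mean square error over all attempts = √((1 − d)·s₁² + d·s₂²), where d is the share lost and s₁ and s₂ are the SDs of retained and lost errors. Assume s₁ = 2 and d = 0.20. With s₂ = 3 it is √(0.8 × 4 + 0.2 × 9) = 2.24; with s₂ = 6 it is √(0.8 × 4 + 0.2 × 36) = 3.22; the reported value is 2.0 in both. None of these SDs or rates is in the protocol, and a blank display has no error to average. The figures show what would be needed for harm, not that harm occurs.

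**7. The passages side by side.** The loss sentence speaks of this kind of study in general and sits in the sample-size paragraph, so it most naturally means incidental movement in the standard test. Motion testing is a separate optional service, and low perfusion is not named in that sentence. Runs without blood draws add nothing to the concern: the listed report and the 200 pairs both rest on arterial values, so such runs do not produce that report, and Methods allows a reference oximeter as comparator.

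**The case for a change.** The strongest reply is that a total found by subtraction is not a reported result. It cannot separate a device that showed nothing from a displayed value that someone discarded, and it gives no reasons. The list of report contents is worded as closed. Methods also lets a manufacturer collect and analyse its own data, with no stated masking to SaO2.

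Much of this is true as description: the split and the reasons are not recoverable from the listed outputs, and no validity rule is written. Three points limit its force. The protocol speaks of readings being lost and nowhere says that displayed values are rejected, so selective rejection is conjecture. For manufacturer-read data, Methods fixes the reading time from the oximeter trace (9 seconds before a sudden change), not from SaO2, and the steady plateau reduces the room for choice. Last, the manual, video, analogue or digital record taken at each sample should show whether a value was on display, so whoever holds that record can make the split when it matters.

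**Conclusion.** This is a gap in reporting detail that a competent analyst fills, and it does not call for a change to the plan. No stated rule produces a wrong bias, SD or root mean square error. Under loss unrelated to error their expected values are unchanged and the SE widens by 2.5% to 11.8% for 12 to 50 readings lost of an assumed 250. Under loss related to error the effect is unknown, because the protocol gives neither a loss rate nor any error distribution. The total lost can be found from the readings table and the blood data, with SD and SE as a rough cross-check.

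The missing split between no reading and a rejected reading matters mainly in the optional motion and low-perfusion tests; the standard steady-state test is much less exposed. Stating samples drawn, paired and lost, with reasons, beside the accuracy results of those tests is ordinary good reporting and needs no new rule. A masked filing step for every recording route would be out of proportion to a problem not shown to occur. The conclusion rests on the readings table being supplied complete and on the blood results covering every sample drawn. The cited guidance may also contain validity rules, but it was not available to check.
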